3. INTRODUCTION

3.1. Cantharidin-induced skin blister assay

The cantharidin blister model was chosen to permit easy access to an acute in vivo inflammatory compartment, in which response to inflammatory challenges might be investigated directly by analysing cellular and soluble components.

Cantharidin is a vesicant (an agent that causes blisters) and a strong inhibitor of protein phosphatases type 1 and 2A (Honkanen, 1993). Following contact with the skin, it is absorbed into the epidermis and activates neutral serine proteases that cause dissolution of desmosomes, leading to acantholysis (the disruption of intercellular bridges between keratinocytes) and intra-epidermal blistering (Bertaux, 1988). The pathology is limited to the suprabasal epidermis and lesions heal without scarring (Moed, 2001). Topical cantharidin solution (0.7%) is used in clinical dermatological practice in Canada for the treatment of warts and molluscum contagiosum and has been demonstrated as an effective treatment, including in children (Noda-Cabrera, 2015). Skin blister induction by cantharidin has been utilised in clinical pharmacology for more than 50 years either as a tool for pharmacokinetic studies or as a model of acute inflammation in human participants. The blister fluid formed after 24 hours of exposure to cantharidin contains inflammatory cells, predominantly neutrophils and monocytes/macrophages, that may be counted (to evaluate leukocyte trafficking and cellular accumulation), analysed by flow cytometry (to perform phenotypic profiling), or used for ex-vivo assays. In parallel, various cytokines, chemokines and other mediators of inflammation may be measured in blister fluid (Day, 2001, Evans, 2006, Harbord, 2006, Evans, 2008). It has been demonstrated that the inflammatory response measured in the cantharidin-induced blister fluid is sensitive to pharmacological manipulation using anti-inflammatory treatment (Morris, 2009). Furthermore, prolonged exposure to cantharidin (40+ hours) allows insight into the resolving phase of acute inflammation (Yagnik, 2000, Philippidis, 2004). In healthy volunteers this phase includes polarisation of monocyte-derived macrophages largely towards a resolving phenotype (Yagnik, 2000, Day, 2001), with enhanced expression of markers such as CD163 and CD206 (Philippidis, 2004) GlaxoSmithKline Document Number (GM2008/00294/00); GlaxoSmithKline Document Number (AM2010/00011/01).

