5. STUDY DESIGN

5.1. Overall Design

This is an exploratory study comprising of 2 parts. In both parts of the study, participants will have 2 sessions. In session 1 (baseline) all participants will have 2 blisters induced on each forearm by application of cantharidin solution (based on method described by Day et al. (Day, 2001)) followed by blood draws and a blister harvest on each forearm at 24 and 48 hours post-induction. After a minimum of 14 days blister healing period, participants will return for a second session (*in vivo* challenge session). This open label study will randomise participants to have either a LPS or GM-CSF *in vivo* challenge (4 completed participants in each group). Participants will then have 2 blisters induced on each forearm by application of cantharidin solution, followed by multiple, timed, blood draws (15 minutes to 48 hours post dose) and a blister harvest on each forearm at 24 and 48 hours post-induction.

In part I of the study, a dose exploration of each of the challenge agents (LPS and GM-CSF) will be required to find a dose that provides a robust inflammatory response. Up to 6 cohorts of 4 participants will be tested and all cohorts will have 2 sessions, as described above. For Part I, an initial cohort of 4 participants (Cohort 1) will proceed with session 1. After their blister healing period, Cohort 1 will return for their session 2 visit in two groups of 2 participants (Group A and Group B) on different days. Group A will be dosed on the same day (one with LPS and one with GM-CSF) and Group B will be dosed on a different day (one participant with LPS and one participant with GM-CSF) after group A. Once all 4 participants have been dosed, a dose escalation meeting will be held to make an assessment of tolerability and inflammatory response from the first Cohort (e.g. the primary endpoints) to determine the dose for Cohort 2. This dose escalation meeting will be held prior to Group A in Cohort 2 proceeding to be dosed with the challenge agents in Session 2. This same dose escalation procedure will continue until a well-tolerated dose for LPS and GM-CSF showing a robust inflammatory response has been identified. Once the well-tolerated dose with robust inflammatory response has been determined, additional participants will be administered this same dose until there are 8 evaluable participants (4 with LPS at the same dose and 4 with GM-CSF at the same dose) completed in Part I.

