9.7.3. Biomarkers in blisters

Biomarkers in blisters will be sampled at 24 and 48 hours post blister induction and collected in polypropylene micro-centrifuge tubes. Cellular and soluble contents will be separated. The volume of the blister sample will be calculated and recorded in the eCRF.

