## 2.2. Study Objective(s) and Endpoint(s)

Objectives	Endpoints
Primary Objectives	Primary Endpoints

 
To compare and define the time course of soluble and cellular inflammatory biomarkers (and urinary prostaglandins for LPS only) following systemic challenge with LPS or GM-CSF in healthy participants
 
	
 
For LPS only: time course and magnitude of upregulation of circulating TNF-<math>\alpha</math> and IL-6 as well as urinary tetranor PGDM
 
For GM-CSF only: time course and magnitude of upregulation of circulating total leukocyte numbers.
 

Secondary Objectives	Secondary Endpoints

 
To compare soluble and cellular inflammatory biomarkers in cantharidin-induced skin blisters at baseline versus systemic challenge with LPS or GM-CSF in healthy participants
 
	
 
Soluble inflammatory biomarkers in skin blisters (may include but not limited to IL-1b, IL-2, IL-6, IL-8, IFN<math>\gamma</math>, TNF-<math>\alpha</math>, MCP-1, GM-CSF, CRP).
 
Blister volumes and differential cell counts (cellular activation markers may include, but not limited to expression of CD16, CD86, CD80, CD163, CD206, CD83, CD40, CD209, HLA-DR in blister leukocytes)
 

 
To define the time course of circulating soluble and cellular inflammatory biomarker upregulation following systemic challenge with LPS or GM-CSF in healthy participants
 
	
 
Time course of regulation of circulating soluble inflammatory biomarkers (may include but is not limited to IL-1b, IL-2, IL-6, IL-8, IFN<math>\gamma</math>, TNF-<math>\alpha</math>, MCP-1, GM-CSF, CRP).
 
Time course of regulation of circulating leukocyte numbers and cellular activation markers (may include, but not limited to expression of CD16, CD86, CD80, CD163, CD206, CD83, CD40, CD209, HLA-DR in circulating leukocytes)
 

Exploratory Objectives	Exploratory Endpoints

 
To compare suitability of blisters sampled at 24 and 48 hours after induction for maximising observed effects of systemic challenge
 
	
 
Primary and Secondary endpoints measured in 24 versus 48 hour blisters
 

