### 5.2. Baseline Definitions

For all endpoints (except as noted in baseline definitions) the baseline value will be the latest pre-dose assessment with a non-missing value, including those from unscheduled visits. If time is not collected, Day 1 assessments are assumed to be taken prior to first dose of challenge and used as baseline.

Parameter	Study Assessments Considered as Baseline				Baseline Used in Data Display
	Screening	Session 1 Day 1	Session 1 Day 2	Session 2 Day 1	
Biomarkers					
LPS: TNF- $\alpha$ , IL6 GM-CSF: WBC (Total leukocyte counts)		X	X	X	Session 2 Day 1 (Pre Blister Induction)
Blood		X			Session 1 Day 1 (Pre Blister Induction)
Blister			X		Session 1 Day 2 (24 HR)
Urine			X		Session 1 Day 2 (Pre Fluid Sampling)
In Vivo LPS or GM-CSF				X	Session 2 Day 1 (Pre Blister Induction)
Safety					
Vital Signs & Temperature	X	X			Session 1 Day 1
ECG	X				Screening
Labs	X	X			Session 1 Day 1

Unless otherwise stated, if baseline data is missing no derivation will be performed and baseline will be set to missing.

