### 7.2.2. Summary Measure

Absolute values and change from baseline of soluble and cellular inflammatory biomarkers across the time course.

Note: In the Interim Analysis, for the biomarkers from skin blister fluid, values will be averaged across arms (left and right) for each participant. These averaged values will be used in tables and figures.

If one of the values is not collected or is missing, then the single value present in the data will be used in tables and figures. Appropriate footnotes will be provided to reflect data are not an average value.

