## 10.7.4. Biomarker Tables

Biomarker Tables					
No.	Population	IDSL / Example Shell	Title	Programming Notes	Deliverable [Priority]
Soluble Inflammatory Mediators					
2.1.	Safety	BIO_T1	Summary of Primary Soluble Inflammatory Mediators in Blood	Page by Treatment and Biomarker	IA [1]
2.2.	Safety	BIO_T1	Summary of Change from Baseline in Primary Soluble Inflammatory Mediators in Blood	Page by Treatment and Biomarker.	IA [1]
2.3.	Safety	BIO_T1	Summary of Secondary Soluble Inflammatory Mediators in Blood	Page by Treatment and Biomarker	IA [1]
2.4.	Safety	BIO_T1	Summary of Change from Baseline in Secondary Soluble Inflammatory Mediators in Blood	Page by Treatment and Biomarker	IA [1]
2.5.	Safety	BIO_T1	Summary of Soluble Inflammatory Mediators from In-Vitro (un)stimulated Blood Pre and Post In-Vivo LPS Challenge	Page by Treatment and Biomarker	IA [1]
2.6.	Safety	BIO_T1	Summary of Soluble Inflammatory Mediators in Blister	Page by Treatment and Biomarker	IA [1]
2.7.	Safety	BIO_T1	Summary of Change from Baseline of Soluble Inflammatory Mediators in Blister	Page by Treatment and Biomarker	IA [1]
2.8.	Safety	BIO_T1	Summary of Soluble Inflammatory Mediators in Urine following LPS Challenge	Page by Treatment and Biomarker	IA [1]
2.9.	Safety	BIO_T1	Summary of Change from Baseline of Soluble Inflammatory Mediators in Urine following LPS Challenge	Page by Treatment and Biomarker	IA [1]
Total Leukocyte Numbers					
2.10.	Safety	BIO_T1	Summary of Cell Numbers in Blood following GM-CSF Challenge	Page by Treatment and Biomarker	IA [1]
2.11.	Safety	BIO_T1	Summary of Change from Baseline in Cell Numbers in Blood	Page by Treatment and	IA [1]

Biomarker Tables					
No.	Population	IDSL / Example Shell	Title	Programming Notes	Deliverable [Priority]
			following GM-CSF Challenge	Biomarker	
Blister Volume					
2.12.	Safety	BIO_T1	Summary of Blister Volume	Page by Treatment	IA [1]
Flow Cytometry					
2.13.	Safety	BIO_T1	Summary of Cell Activation Markers by Flow Cytometry on Monocytes in Blood	Page by Treatment and Biomarker	IA [1]
2.14.	Safety	BIO_T1	Summary of Change from Baseline in Cell Activation Markers by Flow Cytometry on Monocytes in Blood	Page by Treatment and Biomarker	IA [1]
2.15.	Safety	BIO_T1	Summary of Cell Activation Markers by Flow Cytometry on Dendritic Cells in Blood	Page by Treatment and Biomarker	IA [1]

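### The 48-hour blister change from baseline is taken from a 24-hour blister, so it mixes the challenge effect with the blister's own 24-to-48-hour evolution

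*SAP*

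**What the plan says.** SAP 5.2 (Baseline Definitions) names the displayed baseline for blisters as "Session 1 Day 2 (24 HR"). Its table has no column for Session 1 Day 3. The blister row overrides the general rule in the same section: "For all endpoints (except as noted in baseline definitions) the baseline value will be the latest pre-dose assessment with a non-missing value".

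SAP 7.2.2 sets the summary measure for the secondary biomarkers: "Absolute values and change from baseline of soluble and cellular inflammatory biomarkers across the time course". It defines no other blister baseline. SAP 10.7.4 then lists the change tables, for example "Summary of Change from Baseline of Soluble Inflammatory Mediators in Blister" (Table 2.7).

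Protocol 5.1 treats the whole unchallenged session as the reference: "In session 1 (baseline) all participants will have 2 blisters induced on each forearm". It plans harvests at 24 and 48 hours in each session, and Protocol 9.7.3 agrees: "Biomarkers in blisters will be sampled at 24 and 48 hours post blister induction".

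Protocol 3.1 explains why the age of the blister matters: "prolonged exposure to cantharidin (40+ hours) allows insight into the resolving phase of acute inflammation". It adds that CD163 and CD206 expression is enhanced in that phase in healthy volunteers.

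SAP 2.2 carries an exploratory objective that needs a separate contrast at each time: "To compare suitability of blisters sampled at 24 and 48 hours".

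**The concern.** Each participant should supply an unchallenged blister of the same age as each challenged one. The plan uses the younger of the two Session 1 blisters as the reference for both Session 2 harvests. A marker that simply rises between 24 and 48 hours will then look raised by the challenge at 48 hours, and one that falls will hide or reverse a real effect. CD163 and CD206 are direct examples: the protocol expects them to be enhanced in the later phase without any challenge, and SAP 10.3.3 lists both among the blister activation markers.

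Two objectives are touched. The secondary objective compares blister biomarkers at baseline with those after challenge. The exploratory objective asks whether 24-hour or 48-hour blisters show the challenge effect better. For that question the two change scores are not alike, because one is age-matched and the other is not.

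**Working it through.** The point concerns a definition, so the plan states no figure to reproduce. The check traces the baseline rule through the displays and then separates the contrast into its parts.

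**Which displays are affected.** Under SAP 5.2, every blister change uses Session 1 at 24 h. At 48 hours this reaches:

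- mediators: Table 2.7, Figures 2.12 and 2.14, Listing 5;
- activation markers on monocytes: Table 2.20, Figures 2.37 and 2.39, Listing 12;
- activation markers on dendritic cells: Table 2.22, Figures 2.41 and 2.43, Listing 13;
- cell counts: Table 2.24, Figures 2.45 and 2.47, Listing 14.

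Blister volume has only Table 2.12 and Figure 2.23, neither of which shows change. Listing 8 shares the blister listing shell, which has a change column, so the same rule would apply there if that column is filled.

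**Difference scale.** Write S1 and S2 for the sessions. Then

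(S2 at 48 h − S1 at 24 h) = (S2 at 48 h − S1 at 48 h) + (S1 at 48 h − S1 at 24 h).

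The first term on the right is the age-matched challenge contrast. The second is the blister's natural course and has nothing to do with LPS or GM-CSF.

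**Ratio scale.** Let C be the true challenge ratio at 48 h and r the natural 48 h/24 h ratio. The planned contrast estimates C × r. The matched contrast, S2 at 48 h over S1 at 48 h, estimates C for any r.

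**Scale of the bias.** The documents describe the 24-to-48 h change only qualitatively, so r is an assumption and is shown as a range. The column C = 1 means no challenge effect. C = 1.4 is borrowed from the planning ratio in Protocol 10.1, purely as an illustration.

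| Assumed r | Displayed ratio if C = 1 | Displayed ratio if C = 1.4 |
|---|---|---|
| 0.5 | 0.5 | 1.4 × 0.5 = 0.70 |
| 0.7 | 0.7 | 1.4 × 0.7 = 0.98 |
| 1.0 | 1.0 | 1.40 |
| 1.5 | 1.5 | 1.4 × 1.5 = 2.10 |
| 2.0 | 2.0 | 1.4 × 2.0 = 2.80 |

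**The 24 h versus 48 h comparison.** Suppose the challenge effect is 1.4 at both times. The 24-hour change shows 1.40. The 48-hour change shows 2.10 if r = 1.5 and 0.98 if r = 0.7. The apparent preference for one harvest time would come entirely from r.

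**Would the default rule have helped?** The latest pre-dose blister is Session 1 at 48 h. Using it throughout would match the 48-hour contrast and mismatch the 24-hour one. No single blister serves both.

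**What can be recovered from the planned tables.** With complete data, mean(S2 at 48 h − S1 at 24 h) minus mean(S1 at 48 h − S1 at 24 h) equals mean(S2 at 48 h − S1 at 48 h). The SD of the matched change does not follow from the summary tables, because it depends on the covariance of those two changes. It has to be computed from individual data.

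**The case against.** The strongest case on the other side is that the information is not lost and no formal decision uses it. Several parts of this stand.

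- Absolute blister values have their own tables (2.6, 2.19, 2.21, 2.23), individual plots and listings. The shared table shell has a Session 1 Day 3 row, and the figure key includes that visit. With about four participants per agent at the selected dose, a reader can compare like with like by eye.
- This SAP covers dose escalation and the interim only, and a later version is promised for final reporting. The interim is descriptive.
- The numeric Part II criteria in SAP 3.2 use plasma TNF-α and IL-6, urinary tetranor PGDM and total leukocytes, with no blister value. The remaining route is informal: all available biomarker data are considered for the GM-CSF decision and in choosing which biomarkers to assess in Part II.
- A fixed reference has one merit: it lets the change displays show the natural course in Session 1.

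A reader might infer more than the documents support. One inference is that every blister change is biased; the 24-hour contrast is properly matched. Another is that the two objectives rest wholly on change scores, or that the choice between 24 and 48 hours will come out wrong. But SAP 7.2.2 also specifies absolute values, and this version sets out no analysis that makes that choice.

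A third temptation is to turn an assumed drift into a probability of false success under the rule in Protocol 10.1. That fails on every input. No r is given. The SD of 0.394 is the planning value for IL-6, which is not in the interim blister panel. SAP Table 1 says the sample-size methodology no longer applies, and no blister display declares success.

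What the objection does not remove is that the plan's own change score at 48 hours answers a different question from the one in the objective, and nothing else in either document corrects it.

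**Conclusion.** The 48-hour blister change from baseline is wrong as defined. For mediators, activation markers and cell counts it estimates the challenge effect combined with the natural 24-to-48-hour course of the blister. The direction and size of the bias depend on r for each marker. The documents do not give r, so no single figure can be put on it. Protocol 3.1 gives reason to expect that r is not 1, at least for CD163 and CD206.

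The reach is limited to the 48-hour change displays. They inform the secondary blister objective and the exploratory harvest-time objective, and only informally the Part II decisions. The point should be fixed, but it does not invalidate the interim or its numeric Part II criteria.

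**What to change.** In SAP 5.2, define the blister baseline by blister age: Session 1 Day 2 for the Session 2 24-hour blister, and Session 1 Day 3 for the Session 2 48-hour blister. Apply this to Tables 2.7, 2.20, 2.22 and 2.24, to the matching figures and listings, and to the baseline footnote on each. Show the Session 1 24-to-48 h change separately so that the natural course stays visible. Carry the same rule into the final version of the plan.

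The cost is small: one row of the baseline table, some programming and one additional display. The samples are already in the schedule. A participant without a Session 1 48-hour sample would have no 48-hour change, which fits the existing SAP 5.2 rule that a missing baseline stays missing. With groups this small, the number contributing to each contrast should be shown.

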**5.3. Examination of Covariates, Other Strata and Subgroups**

**5.3.1. Covariates and Other Strata**

There are no planned covariates or other strata that will be used in descriptive summaries and statistical analyses, if conducted.

**5.3.2. Examination of Subgroups**

There are no planned sub-group analyses.

**5.4. Multiple Comparisons and Multiplicity**

Analyses, if conducted will not be subject to any multiplicity adjustment.

**5.5. Other Considerations for Data Analyses and Data Handling Conventions**

Other considerations for data analyses and data handling conventions for Interim Reporting are outlined in the appendices:

Section	Component
10.2	Appendix 2: Data Display Standards & Handling Conventions
10.3	Appendix 3: Derived and Transformed Data
10.4	Appendix 4: Reporting Standards for Missing Data
10.5	Appendix 5: Values of Potential Clinical Importance

## **6. STUDY POPULATION ANALYSES**

### **6.1. Overview of Planned Study Population Analyses**

The study population analyses will be based on the “Enrolled” population, unless otherwise specified. Screen failures will be listed based on the “Screened” population.

Study population analyses including analyses of subject’s disposition, protocol deviations, demographic and baseline characteristics, prior and concomitant medications, and exposure and treatment compliance will be based on GSK IDSL Data Standards. Details of the planned displays are presented in [Appendix 7: List of Data Displays](#).

For the Interim Analysis, only a Summary and Listing of Demographic Characteristics will be presented.

## 7. EFFICACY ANALYSES

### 7.1. Primary Biomarker Analyses

Unless otherwise stated, analyses will apply to the interim analyses.

#### 7.1.1. Endpoint / Variables

Challenge	Endpoint
LPS	Time course and magnitude of upregulation of circulating TNF- $\alpha$ and IL-6 as well as urinary tetranor PGDM
GM-CSF	Time course and magnitude of upregulation of circulating total leukocyte numbers.

#### 7.1.2. Summary Measure

Challenge	Endpoint
LPS	Absolute values and change from baseline in TNF- $\alpha$ , IL-6 and PGDM across the time course Baseline: 
 
• TNF-<math>\alpha</math>, IL-6: Session 2: Day 1 (Pre Blister Induction)
 
• PGDM: Session 1 Day 2 (Pre Fluid Sampling)
 

GM-CSF	Absolute values and change from baseline in total leukocyte across the time course 
 
• Baseline = Session 2: Day 1 (Pre Blister Induction)
 

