5.5.2. LPS

The initial dose level for LPS is proposed to be 0.5 ng/kg (bioactivity of proposed batch LPS is 6 EU / ng, therefore a dose of 3.0 EU / kg). This dose is associated with a measurable systemic cytokine response but is well tolerated based on the literature. Participants will be hydrated prior to administration of LPS with normal saline at a rate of 250 mL/hr for 4 hours prior to dosing and 8 hours after dosing.

If dose escalation is required to achieve a robust (well tolerated) systemic cytokine response, then this will proceed in increments not exceeding a doubling of the previous dose; the highest permitted dose will be 4 ng/kg. (i.e. 24 EU/kg). Dose escalation will be guided by 1) safety and tolerability 2) the systemic cytokine response although other secondary and exploratory markers may also be taken into account. The goal is to achieve informative biomarker excursions with absent or trivial symptoms experienced by participants.

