9.7.2. Biomarkers in urine

The pre-challenge urine sample will be collected during session 1. The post-challenge urine samples will be collected during session 2 after LPS challenge. In session 2, participants will be encouraged to pass urine immediately before LPS challenge dose and urine voids will be collected from after LPS until 12 hours post-LPS and the time of the urine collection will be recorded. These samples will be collected for measurement of tetranor-PGDM and other inflammatory mediators. Tetranor-PGDM is the stable urinary metabolite of the prostaglandin PGD2. While tetranor-PGDM has very low natural abundance in normal healthy individuals, it has been shown to be elevated in the urine of patients with Duchenne muscular dystrophy. Elevation of urinary tetranor-PGDM in normal healthy volunteers through LPS challenge would allow for evaluation of target engagement in that population Tetranor-PGDM and related metabolite will be measure by mass spectroscopy as samples are collected.

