Dose Escalation Criteria	
Below is the Dose Escalation Criteria decided by the study team                      If only one participant hits stopping criteria then there will be a presumption of stopping escalation, unless in the judgement of the team further escalation would provide additional scientific value to the study without materially impacting on participant wellbeing.
 
LPS: STOP dose escalation, IF:
 
 
• Peak plasma/serum level of TNF-<math>\alpha</math> <math>\geq</math> 100 pg/mL (minimum increase of 75 pg/ml from baseline) AND
 
• Peak plasma/serum level of IL-6 <math>\geq</math> 200 pg/mL (minimum increase of 100 pg/ml from baseline) AND
 
• Urinary tetranor PGDM 3x over baseline in urine OR
 
• Presence of adverse clinical signs (fever, HR + others) which, in the opinion of the investigator, pose an unacceptable risk to participants were dose escalation to proceed. Examples may include, but are not limited to:                             
 
○ Rigors
 
○ Meningeal symptoms of moderate severity
 
○ Vomiting
 
○ Clinically significant hypotension, hypertension, tachycardia or bradycardia
 
 
 
 
GM-CSF: STOP dose escalation IF:
 
 
• Max change of circulating total leukocyte counts increase by 5 giga/L OR
 
• Presence of adverse clinical signs (fever, HR + others) which, in the opinion of the investigator, pose an unacceptable risk to participants were dose escalation to proceed. Examples may include, but are not limited to:                             
 
○ Rigors
 
○ Meningeal symptoms of moderate severity
 
○ Vomiting
 
○ Clinically significant hypotension, hypertension, tachycardia or bradycardia
 
 
 
• Elevation of platelet count above 500 x 10^9/L
 

Dose Escalation Decision	
 
• Following each dose escalation meeting, the decision to STOP or dose escalate for each challenge agent was documented,
 
• An optimum dose of 0.75 ng/kg for LPS and 60 ug/m^2 for GM-CSF was identified.
 

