	Matrix metalloproteinase 9	MMP9	CONC/ MSD/ PG/ML
Soluble Inflammatory Mediators (Urine) Primary	Tetranor-Prostaglandin E Metabolite	TETPGDM	CONC/ LCMS/ PG/ML
	Tetranor-Prostaglandin D Metabolite	TETPGEM	CONC/ LCMS/ PG/ML
Cell Numbers (Blood) Primary	White blood cells	WBC	TNCELL/ FLWCY/ CELLS/ML
Blister Volume (Blister)	Blister Fluid	BLISTFL	VOL/ WTDENC/ UL
Flow Cytometry  Cell Activation Markers on Monocytes (Blister and Blood)	CD16+	CD16	C6/ FLWCY/ MNFI
	CD86+	CD86	C6/ FLWCY/ MNFI
	CD80 molecule	CD80	C6/ FLWCY/ MNFI
	CD163+	CD163	C6/ FLWCY/ MNFI
	CD206+	CD206	C6/ FLWCY/ MNFI
	CD83 molecule	CD83	C6/ FLWCY/ MNFI

Name (Analyte)	Biomarker Detailed Name	BICATCD	BITESTCD/ BIMETHCD/ BIORRESU
	CD40	CD40	C6/ FLWCY/ MNFI
	CD209+	CD209	C6/ FLWCY/ MNFI
	HLA-DR	HLADR	C6/ FLWCY/ MNFI
	CD40+/CD80+	CDX690	%MONO/ FLWCY/ %
Flow Cytometry  Cell Activation Markers on Dendritic Cells  (Blister and Blood)	CD16+	CD16	R1/ FLWCY/ MNFI
	CD86+	CD86	R1/ FLWCY/ MNFI
	CD80 molecule	CD80	R1/ FLWCY/ MNFI
	CD163+	CD163	R1/ FLWCY/ MNFI
	CD206+	CD206	R1/ FLWCY/ MNFI
	CD83 molecule	CD83	R1/ FLWCY/ MNFI
	CD40	CD40	R1/ FLWCY/ MNFI
	CD209+	CD209	R1/ FLWCY/ MNFI
	HLA-DR	HLADR	R1/ FLWCY/ MNFI
CD40+/CD80+	CDX690	%TDC/ FLWCY/ %	
Flow Cytometry	Neutrophils	NEUT	TNCELL/ FLWCY/ CELLS/ML

Name (Analyte)	Biomarker Detailed Name	BICATCD	BITESTCD/ BIMETHCD/ BIORRESU
Cell Counts (Blood)	Lymphocytes	LYMPH	TNCELL/ FLWCY/ CELLS/ML
	Monocytes	MONO	TNCELL/ FLWCY/ CELLS/ML
	B Cells	BCELL	TNCELL/ FLWCY/ CELLS/ML
	CD45+ CD3- CD56+ (NK Cells)	CDX223	TNCELL/ FLWCY/ CELLS/ML
	CD45+ CD3+ CD56+ (NKT Cells)	CDX224	TNCELL/ FLWCY/ CELLS/ML
	Total T Cells	TTCELL	TNCELL/ FLWCY/ CELLS/ML
	CD4+	CD4	TNCELL/ FLWCY/ CELLS/ML
	CD8+	CD8	TNCELL/ FLWCY/ CELLS/ML
	CD14+CD16+ Monocytes	CDX469	TNCELL/ FLWCY/ CELLS/ML
	CD14+CD16- Monocytes	CDX471	TNCELL/ FLWCY/ CELLS/ML
	CD14-CD16+ Monocytes	CDX611	TNCELL/ FLWCY/ CELLS/ML
Flow Cytometry  Cell Counts (Blister)	Neutrophils	NEUT	TNCELL/ FLWCY/ CELLS/ML or 10  CELLS/BLISTER
Note: These biomarkers are measured in 2 units –	Lymphocytes	LYMPH	TNCELL/ FLWCY/ CELLS/ML or 10  CELLS/BLISTER

Name (Analyte)	Biomarker Detailed Name	BICATCD	BITESTCD/ BIMETHCD/ BIORRESU
Cells/ml and 10  Cells/Blister	Monocytes	MONO	TNCELL/ FLWCY/ CELLS/ML or 10  CELLS/BLISTER
	B Cells	BCELL	TNCELL/ FLWCY/ CELLS/ML or 10  CELLS/BLISTER
	CD45+ CD3- CD56+ (NK Cells)	CDX223	TNCELL/ FLWCY/ CELLS/ML or 10  CELLS/BLISTER

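### Urinary tetranor PGDM is compared as an uncorrected concentration between a Session 1 sample taken without IV fluid and post-LPS voids collected mostly under saline infusion, so change from baseline mixes excretion with urine flow

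*SAP*

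**What the plan says.** - **Endpoint.** SAP 7.1.1 lists the LPS primary endpoints as circulating TNF-α and IL-6 "as well as urinary tetranor PGDM".
- **Summary measure.** SAP 7.1.2 begins "Absolute values and change from baseline in TNF" and extends the same treatment to IL-6 and PGDM. The two cytokines take a Session 2 Day 1 baseline. The urine marker takes "PGDM: Session 1 Day 2 (Pre Fluid Sampling". SAP 5.2 gives the same urine baseline, "Session 1 Day 2 (Pre Fluid Sampling".
- **Unit.** The biomarker table in SAP 10.3.3 records the urinary metabolites as "CONC/ LCMS/ PG/ML", a mass-spectrometry concentration.
- **Urine collection.** Protocol 9.7.2 states that "The pre-challenge urine sample will be collected during session 1". In Session 2, participants are encouraged to empty the bladder just before LPS. Collection covers the voids after LPS, up to 12 hours, with the time of each recorded.
- **Hydration.** Protocol 5.5.2 gives LPS participants "normal saline at a rate of 250 mL/hr for 4 hours prior to dosing and 8 hours after dosing". The schedule of activities places this on Session 2 Day 1 only.
- **Decision rules.** One of the three biomarker conditions for stopping LPS escalation in SAP 3.1 is "Urinary tetranor PGDM 3x over baseline in urine". SAP 3.2 opens Part II for LPS if at least one participant at the chosen dose has a largest PGDM rise below 1.3x and also TNF-α and IL-6 rises each below 50 pg/mL.

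**The concern.** A urine concentration is the amount excreted per hour divided by the volume of urine produced per hour. If urine flow differs between the baseline and post-challenge samples, the change in concentration reflects water output as well as PGDM response. Here the difference is built into the schedule: no infusion around the baseline sample, and 3 L of saline around the post-LPS voids.

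Three things that are still open depend on this comparison:

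- the reported size and time course of a primary endpoint;
- the PGDM condition for Part II, which dilution makes easier to meet;
- the estimates for future work. Protocol 9.7.2 wants PGDM raised by LPS so that target engagement can be evaluated, and Protocol 10.1 looks to Part I for in-house PGDM estimates.

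**Working it through.** **No planned figure to reproduce.** Protocol 10.1 says PGDM estimates are very limited. It gives no expected rise, standard deviation or probability of success for this endpoint.

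**Inputs from the documents.**
- Saline: 250 mL/h × 4 h = 1,000 mL before LPS and 250 mL/h × 8 h = 2,000 mL after, 3,000 mL in all. None is scheduled in Session 1.
- Post-LPS collection: 12 h, of which 8 h (two thirds) are under saline.
- Corrections: none found. Creatinine appears among the clinical chemistry tests and specific gravity under routine urinalysis (Protocol Appendix 2). Neither is tied to the urine samples used for PGDM. Void volume is not said to be recorded.
- In SAP 10.3.3 the names and codes of the D and E metabolites appear crossed. Both rows carry the same unit, so this does not affect the point.

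**Formula.** Let Q1 be urine flow at the Session 1 sample, Q2 flow at the post-LPS void, and D = Q2/Q1. Then:

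observed fold in pg/mL = true fold in excretion ÷ D

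**Assumed flows.** The documents give none, so a range is shown.

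| Case | Q1 (mL/h) | Q2 (mL/h) | D | True 3x reads as | True rise that reads as 1.3x |
|---|---|---|---|---|---|
| Low: 10% of the infusion appears in urine | 100 | 100 + 0.10 × 250 = 125 | 1.25 | 3/1.25 = 2.4x | 1.3 × 1.25 = 1.6x |
| Middle: 50% appears | 60 | 60 + 0.50 × 250 = 185 | 3.08 | 3/3.08 = 0.97x | 1.3 × 3.08 = 4.0x |
| High: flow equals the infusion rate | 42 | 250 | 5.95 | 3/5.95 = 0.50x | 1.3 × 5.95 = 7.7x |

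A true 3x rise reads below the 1.3x limit once D exceeds 3/1.3 = 2.3. A more extreme assumption (Q1 = 30 mL/h, all saline excreted) gives D = 280/30 = 9.3 and a reading of 0.32x.

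**Time course.** D is not constant. Suppose PGDM excretion does not change at all. While saline runs, the concentration reads 1/D of baseline: 0.80x, 0.32x or 0.17x in the three cases. If flow then falls back towards Q1 after hour 8, the reading drifts up towards 1.0x. A dip followed by a late recovery could therefore appear with no PGDM response.

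**Reach of the Part II rule.** At worst, dilution makes the PGDM condition true for every participant. The three-part rule then reduces to the two cytokine conditions. A participant whose TNF-α or IL-6 rise reaches 50 pg/mL cannot trigger Part II, whatever the PGDM reading.

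**The case against.** The strongest reply is that the size of the effect is wholly assumed. No urine flow, void volume or expected PGDM rise is given, and oral intake is uncontrolled in both sessions. Protocol 3.4.1 also names volume depletion after overnight fasting when explaining the vagal-reaction risk, so urine output under saline could be modest. This stands. It is why the range starts at 1.25 and why the direction is called likely. A reader might infer that PGDM rises are shown to be understated by a known factor; the documents do not support that.

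Saline also stops at 8 hours, and the Part II rule takes the largest rise over all time points. A less diluted void between 8 and 12 hours could partly escape the bias. This stands for the maximum, but not for the time course, which is itself part of the endpoint.

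A reader might also infer that dilution drove LPS escalation by keeping the 3x condition from being met. SAP 3.1 describes escalation as finished, with 0.75 ng/kg selected. The 3x condition was joined by AND to both cytokines, clinical signs were a separate route to stopping, and no PGDM values are shown. Nothing in the documents shows that PGDM changed a dose decision, and changing the analysis now could not alter one.

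The study is exploratory and descriptive, without hypotheses, and this SAP version covers only escalation and the interim; final reporting has a later version. That lowers the stakes and leaves room to correct the analysis. It does not remove the problem from the interim outputs, and creatinine can be measured only while urine remains.

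The Session 1 baseline is the protocol's deliberate choice, and the Session 2 urine is also collected after cantharidin. Blister inflammation in the baseline sample is therefore not pressed here. The point concerns hydration.

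**Conclusion.** The concern holds in this form. A primary endpoint is compared as a raw concentration across two sessions with different scheduled IV fluid, with no correction in either document. The confounding follows from the plan as written. Its direction, probably downward and strongest during the infusion, is inferred from the saline schedule. Its size rests on assumed flows: for a 1.25- to 6-fold rise in urine flow, a true 3x rise in excretion reads as about 2.4x to 0.5x.

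The live consequences are the reported PGDM endpoint, the PGDM condition for Part II, and the estimates handed to later studies. Dilution makes the Part II condition easier to meet but cannot decide Part II alone, because both cytokine conditions must also be met.

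**What to change.** 1. **All PGDM urine samples.** Measure urinary creatinine and analyse PGDM per mg creatinine. Both concentrations are divided by the same flow, so flow cancels, provided creatinine excretion is reasonably stable between samples. Apply the 1.3x Part II criterion on this scale and say so in SAP 3.2, 7.1.2 and 10.3.3.
2. **Any further LPS participants.** Keep and assay the void passed immediately before LPS in Session 2, and make it the primary PGDM baseline. Show the Session 1 sample descriptively. The new baseline is same-day but not identically hydrated: it follows about 1 L of saline, so creatinine correction is still needed.
3. **Part I participants.** Creatinine-correct the Session 1 and post-LPS samples where urine remains. This cannot be presumed. Protocol 9.7.2 has PGDM measured as samples come in, the general storage rule in Protocol section 9 does not show that urine was kept, and the pre-LPS void is not described as collected.
4. **Where no urine remains.** State that uncorrected PGDM changes are confounded by hydration, and do not rely on PGDM in the Part II decision. The decision then loses whatever check PGDM would have added to the cytokine conditions.

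The cost is a routine creatinine assay, one extra PGDM assay per further LPS participant, SAP wording, and slight added assay noise. No change to hydration or dosing is implied.
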